9.2 SAMPLE SIZE DETERMINATION

To evaluate genotype sensitivity of [¹⁸F]SF12051 we calculated the percent difference in binding values necessary to differentiate between HABs, MABs and LABs. This was based on our previous results with [¹¹C]ER176 in healthy volunteers of different genotypes (Ikawa et al 2016). The mean V_T of HH subjects (HABs; n = 9) for whole brain was 4.5 mL/cm³ with a standard deviation of 1.4 mL/cm³. In addition, the V_T of HH subjects was 40% higher than the V_T of HL subjects. Assuming the same SD for [¹¹C]ER176 and [¹⁸F]SF12051, we can calculate how much of a difference in mean V_T can be detected between genotypes. Power analysis based on V_T of HH subjects from [¹¹C]PBR28 scans showed that with a sample size of 10 for each binder group, a power of 80% and alpha of 0.05 the percent difference to be detected from the mean value of a HAB is 40%. That is, the difference in mean V_T between HH and other genotypes should be >40% for it reach a statistical significance with a sample size of 10. Therefore, we require a recruitment of 34 in total for HABs, MABs and LABs under Phase 2 and 4 considering some withdrawals.

We wish to balance the number of subjects in the three TSPO genotypes: HAB, MAB, and LAB. Although all genotypes will be accepted during the initial scans, we will likely require specific genotypes toward the end of the scan, especially for the rare LABs. For this reason, we may select individuals based on TSPO genotype in order to have roughly equal number of subjects in the three groups.

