1.1 SYNOPSIS

| | |
|---|---|
| Title: | Assessment of [¹⁸ F]SF12051 for Imaging the 18-kDa Translocator Protein (TSPO) in Brain and Whole Body of Healthy Subjects |
| Study Description: | This study is intended to provide information on the novel [¹⁸ F]SF12051 radioligand and its ability to localize and measure TSPO in the brain and body of healthy individuals. |
| Objectives: | 
Primary Objective: To study the brain uptake of [¹⁸F]SF12051 and perform kinetic modeling of the [¹⁸F]SF12051 in the three different TSPO genotypes.
 
Secondary Objectives: To study the brain retest characteristics, biodistribution and dosimetry of [¹⁸F]SF12051 in healthy subjects.
 |
| Endpoints: | 
Primary Endpoint: The distribution volume of the radioligand and stability over time calculated with compartmental modeling, attention paid to differences in mean distribution volumes between TSPO genotypes for determining genotype sensitivity.
 
Secondary Endpoints: Retest variability and reliability and organ-time-activity curves to determine biodistribution and dosimetry.
 |
| Study Population: | Up to forty-five (45) healthy male and female volunteers (18 years and older) of the three different TSPO genotypes for brain and whole-body imaging. |
| Phase: | N/A |
| Description of Sites/Facilities | Screening and PET imaging will be performed at the NIH Clinical Center. |
| Enrolling Participants: | |
| Description of Study Intervention: | Arterial line, PET scan, and brain MRI scan for absolute quantification of TSPO. Blood drawn from all subjects to determine TSPO genotype. |
| Study Duration: | 3 years |
| Participant Duration: | 1-4 visits, 2-6 hours per visit. |

Abbreviated Title: [¹⁸F]SF12051 in Healthy Subjects

Version Date: 12/05/23

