We predict that the new ¹⁸F-radioligand will be like [¹¹C]ER176 and, therefore, that it *will* be sensitive to genotype. Even though [¹¹C]ER176 is sensitive to genotype, it provides time-stable values of receptor binding. Thus for [¹¹C]ER176 and presumably for [¹⁸F]SF12051, LAB subjects need not be excluded a priori, but the results must be corrected a posteriori. If [¹⁸F]SF12051 values of receptor binding are unstable in LABs, it would still be an improvement over current ¹¹C-radioligands and can be used at more sites because of the longer half-life of ¹⁸F compared to ¹¹C.”

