4 STUDY DESIGN

4.1 OVERALL DESIGN

- **Site:** This single-site study will be conducted at the NIH Clinical Center.
- **Hypothesis:** We hypothesize that [¹⁸F]SF12051 will have satisfactory distribution regardless of genotype, acceptable retest variability and reliability, and dosimetry typical of ¹⁸F-labeled radioligands.
- **Phase:** Phase 1
- **Type of Design:** Study is neither randomized nor placebo-controlled; exploratory study.
- **Study Groups:** Healthy volunteers
- **Study intervention:** Brain and body PET scans with [¹⁸F]SF12051 and brain MRI.
- **Interim Analysis:** None
- **Stratifications:** None

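### Section 9.2 turns a correct 80%-power detectable difference (about 40% of the HAB mean) into a significance threshold, and does not say that the ER176 40% it cites has a different base and only about 50% power

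*Combined protocol and SAP*

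**What the plan says.** Section 9.2 introduces its calculation by saying "we calculated the percent difference in binding values necessary to differentiate between HABs, MABs and LABs". It gives a whole-brain mean V_T of 4.5 mL/cm³ (SD 1.4, n = 9) for HH subjects with [¹¹C]ER176. It adds that "the V_T of HH subjects was 40% higher than the V_T of HL subjects" and carries the SD over to [¹⁸F]SF12051.

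The result is then attributed to another tracer: "Power analysis based on V_T of HH subjects from" [¹¹C]PBR28 scans. With 10 per binder group, 80% power and alpha 0.05, "the percent difference to be detected from the mean value of a HAB is 40"%. The next sentence restates this as a difference that "should be >40% for it reach a statistical significance with a sample size of 10". Recruitment of 34 across Phases 2 and 4 follows from it.

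Elsewhere, the Synopsis (1.1) describes the primary endpoint with "attention paid to differences in mean distribution volumes between TSPO genotypes for determining genotype sensitivity". Section 9.4.2 reports the primary endpoint as mean ± SD, and section 9.4.7 analyses the genotype groups separately.

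**The concern.** Three things in one paragraph do not fit together.

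- **Threshold.** A true difference that a design detects with 80% power is larger than the smallest observed difference that gives p < 0.05. Section 9.2 equates the two.
- **Base.** The ER176 effect is a percentage of the HL mean, while the detectable difference is a percentage of the HAB mean. Both are 40%, they stand a few sentences apart, and nothing says that they are different differences.
- **Source.** The inputs shown are ER176 values, but the power analysis is credited to PBR28, for which no mean or SD is given.

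What is at stake is how the genotype comparison is read. Section 2.1 says "We predict that the new ¹⁸F-radioligand will be like [¹¹C]ER176", so an ER176-sized gap is the sponsor's own expectation. Sections 4.1 and 9.1, however, word their hypotheses as holding regardless of genotype. Someone relying on section 9.2 could dismiss an observed HAB–MAB difference of 30–40%, or take a non-significant one as support for genotype insensitivity.

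**Working it through.** **Inputs from section 9.2:** HAB mean 4.5 mL/cm³, SD 1.4, n = 10 per group, power 80%, alpha 0.05, HH = 1.40 × HL.

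**Assumptions, not stated in the plan:** a two-sided test of two independent means, the same SD in each genotype, and an SF12051 HAB mean of 4.5 (section 9.2 carries over only the SD).

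**1. The plan's own figure.** SE of a difference = 1.4 × √(2/10) = 0.626.
- Normal: (1.960 + 0.842) × 0.626 = 1.754 mL/cm³; 1.754/4.5 = 39.0%.
- t test (noncentral t, 18 df): 1.855 mL/cm³; 1.855/4.5 = 41.2%.

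The stated 40% is reproduced. A one-sided t test would give 36.0%, so two-sided fits better.

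**2. The significance threshold.** Smallest observed difference with p < 0.05:
- Normal: 1.960 × 0.626 = 1.227, or 27.3% of 4.5.
- t test: 2.101 × 0.626 = 1.315, or 29.2% of 4.5.

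An observed 40% is 0.40 × 4.5 = 1.80 mL/cm³, so t = 1.80/0.626 = 2.875 and p = 0.010.

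**3. The two 40% figures on one base.**
- ER176: HL = 4.5/1.4 = 3.21; gap = 4.5 − 3.21 = 1.29 mL/cm³; 1.286/4.5 = 28.6% of the HAB mean.
- Detectable: 1.80 mL/cm³ leaves a comparator mean of 2.70; 4.5/2.70 = 1.67, so HAB is about 67% higher than the comparator.

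**4. Power at n = 10 per group.**

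| Case | t test | Normal |
|---|---|---|
| 1.80 mL/cm³, two-sided, common SD | 78% | 82% |
| ER176 gap 1.29, two-sided, common SD | 49% | 54% |
| ER176 gap, one-sided, common SD | 63% | 66% |
| ER176 gap, two-sided, SD proportional to mean (1.4 and 1.0) | 61% | 66% |
| ER176 gap, one-sided, SD proportional to mean | 73% | 76% |

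No ER176-gap case reaches 80%. If all 34 were evaluable (about 11.3 per group), the two-sided, common-SD power would be 55–59%. Only the last row's assumptions would then come near 80% (78–81%).

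**5. Dependence on the HAB mean.** With SD 1.4 held fixed and a gap of 28.6% of the HAB mean, two-sided t power is 33% for a HAB mean of 3.5 (gap 1.00) and 74% for 6.0 (gap 1.71). The 3.5 and 6.0 are illustrative. In mL/cm³ the detectable difference does not move with the mean.

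**6. Source.** ER176 inputs reproduce the 40%. Because no PBR28 mean or SD is shown, this does not settle whether the tracer label or the displayed inputs are out of place.

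**The case against.** The strongest reply is that nothing has been miscalculated. The 40% is right, and the paragraph names its base as the HAB mean. It never claims 80% power for the HH–HL gap. The sentence about significance begins as a paraphrase of the power statement, so it can be taken as loose wording for the detectable true difference. Section 4.1 says "Study is neither randomized nor placebo-controlled; exploratory study"; the primary endpoint is summarised as mean ± SD, no pairwise test is named, and no passage applies 40% to observed means. Section 2.1 already expects genotype sensitivity and correction after the fact, which makes a null HAB–MAB result less likely to be misread.

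Most of this stands, and it limits the consequence. A reader might infer that the study was sized for the ER176 HAB–MAB gap and falls short of a stated 80%, or that an observed difference under 40% will be declared absent. The documents support neither: the plan states no power for that gap and adopts no such rule.

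The loose-wording defence does not save the sentence itself. It says in terms that 40% is what significance requires, in the paragraph that justifies recruiting 34 people to judge genotype sensitivity, and on that paragraph's inputs this is untrue. Naming the HAB base also does not tell the reader that the ER176 40% just cited is only 28.6% on that base.

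**Conclusion.** The detectable difference in section 9.2 is correct; its restatement as a significance threshold is not. Under a two-sided 0.05 test with SD 1.4 and 10 per group, significance starts at about 1.23–1.32 mL/cm³ (27–29% of 4.5), against the 1.80 mL/cm³ implied by 40%. Power is 78–82% for 1.80 mL/cm³ but about 49–54% for the ER176 gap of 1.29, and at n = 10 it stays below 80% under the one-sided and SD-proportional variants (at most 76%).

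These percentages rest on a HAB mean of 4.5 for the new tracer. The shortfall is shown for HAB versus MAB only, because section 9.2 gives no LAB mean. The effect is on interpretation. It would be tempting to conclude that the trial needs more participants, but the plan is exploratory, summarises its primary endpoint descriptively and promises no power for this contrast, so these documents do not require a larger N.

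**What to change.** Delete the sentence that gives more than 40% as the condition for statistical significance, and do not put another fixed cut-off in its place. Replace it with text such as:

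> With 10 per genotype, SD 1.4 mL/cm³ and two-sided alpha 0.05 there is about 80% power for a true difference of about 1.8 mL/cm³ (40% of a HAB mean of 4.5, i.e. HAB about 67% higher than the comparator). Power for a difference the size of the ER176 HH–HL gap (about 1.3 mL/cm³, 28.6% of 4.5) is about 50%, so absence of a clear HAB–MAB difference, however compared, will not be taken as evidence of genotype insensitivity.

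The sponsor should confirm that the test was meant to be two-sided and reconcile the tracer named for the power analysis (PBR28) with the mean and SD shown (ER176). If PBR28 inputs were in fact used, they should be stated and the figures recomputed from them.

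The cost is the rewording of one paragraph. Sample size, procedures and participants are unaffected. The one drawback is that the plan then states openly that power for an ER176-sized HAB–MAB difference is modest.

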9.3 POPULATIONS FOR ANALYSES

All subjects are healthy volunteers.

9.3.1 Evaluable for toxicity

No toxicity is expected from the radioligand; nevertheless, safety will be monitored as described in Section 8.3.

9.3.2 Evaluable for objective response

No therapeutic response is expected from the radioligand as we are testing a diagnostic agent at sub-pharmacological doses.

9.3.3 Evaluable Non-Target Disease Response

Not Applicable.

9.4 STATISTICAL ANALYSES

9.4.1 General Approach

Brain imaging data will be analyzed with kinetic modeling. PET and MRI scans will be coregistered for anatomic definition of regions of interest. SUV will be calculated in various brain regions. Parametric images will be created using PMOD software (PMOD Technologies Ltd., Zurich, Switzerland). The kinetic modeling will give us the [¹⁸F]SF12051 binding values, and their identifiability and stability over time.

In whole body imaging studies, organ time-activity curves will be obtained from the dynamic PET images and used to calculate organ residence times. Residence time of the urinary bladder may be calculated using a dynamic bladder model (12). The residence times will be used in OLINDA/EXM (<http://www.doseinfo-radar.com/OLINDA.html>) to obtain radiation-absorbed dose estimates.

To consider inter-subject variability, radiation absorbed doses are usually estimated from approximately 6-8 subjects (13-15). To also take into account possible gender differences, we propose to study approximately an equal number of male and female subjects in the whole-body imaging study. In addition, we plan at least 3 subjects for each binder group (9 subjects in total). Considering the requirement of one subject for the initial Phase 1 and any possible withdrawals, we seek a total of 10 subjects for Phase 3.

9.4.2 Analysis of the Primary Endpoints

The outcome measure for the primary endpoint will be the total distribution volume and summarized as mean \pm SD.

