9.4.7 Sub-Group Analyses

The different genotype groups will be analyzed separately.

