9.4.7.1 Tabulation of individual Participant Data

Individual participant data will be listed by measure and timepoint.

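### Section 9.2 misstates a 40% difference in V_T as the one needed for significance (about 29% suffices), and section 9.4 plans no estimate of the genotype difference the cohort was sized on

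*Combined protocol and SAP*

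**What the plan says.** The synopsis (section 1.1) gives the primary endpoint as distribution volume and its stability over time, with "attention paid to differences in mean distribution volumes between TSPO genotypes for determining genotype sensitivity".

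Section 9.2 sizes the Phase 2 and Phase 4 brain cohort on that difference. It cites ER176 whole-brain results: HH mean V_T 4.5 mL/cm³, SD 1.4, n = 9, and "the V_T of HH subjects was 40% higher than the V_T of HL subjects". It then reports a power analysis, attributed to PBR28 scans, with 10 per binder group: "a power of 80% and alpha of 0.05 the percent difference to be detected from the mean value of a HAB is 40" per cent. It glosses this by saying that "the difference in mean V_T between HH and other genotypes should be >40% for it reach a statistical significance" at that sample size. Recruitment is set at 34 to allow for withdrawals.

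Section 9.4.2 reads "The outcome measure for the primary endpoint will be the total distribution volume and summarized as mean" ± SD. Section 9.4.7 adds "The different genotype groups will be analyzed separately". Section 9.4.7.1 adds "Individual participant data will be listed by measure and timepoint". Section 9.4.8 plans no exploratory analyses. Nothing in 9.4 names a difference between genotypes, an interval for one, or a test.

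**The concern.** There are two linked problems.

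First, 9.2 treats the difference detectable with 80% power as if it were the significance threshold. A reader who applied the sentence would call an observed difference of 30% to 40% non-significant when it would in fact have p<0.05, and might then describe the ligand as insensitive to genotype. Section 9.2 also contains two figures of 40% on different bases, one relative to the HL mean and one relative to the HAB mean. Because they look alike, the section can be read as offering 80% power for a difference the size of the ER176 one.

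Second, the comparison that justified the cohort size does not appear in the analysis section. Per-genotype summaries are planned, but no estimate of the difference and no statement of its uncertainty. Phase 4 participants have two scans and Phase 2 participants one, so which value represents a Phase 4 participant is also undefined.

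**Working it through.** **Inputs, all from 9.2:** HAB (HH) mean 4.5; SD 1.4; 10 per genotype; 80% power; alpha 0.05; ER176 HH/HL ratio 1.40.

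**Assumptions:** two-sided test (9.2 does not say) and, unless stated, SD 1.4 in every genotype. Section 9.2 assumes the same SD for the two ligands, which is not the same as equal SD across genotypes, and it gives no MAB or LAB SD.

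**1. Reproduce the 40%.**
- SE of a difference, 10 v 10: 1.4 × √(2/10) = 0.626.
- Normal approximation: 0.626 × (1.960 + 0.842) = 1.754, which is 39.0% of 4.5.
- Noncentral t: 1.855 (41.2%) with 18 df, or 1.820 (40.4%) with 27 df if the SD is pooled over three groups.
- Power at exactly 40% (1.8 mL/cm³): 78% (18 df) or 79% (27 df).
- One-sided alpha 0.05 would give 34.6% (z) or 36.0% (t), so the two-sided version is the one that matches.

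The 40% is therefore sound as the true difference detectable with about 80% power.

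**2. Find the significance threshold.**
- 18 df: 2.101 × 0.626 = 1.315, which is 29.2% of 4.5.
- 27 df: 2.052 × 0.626 = 1.285, which is 28.5%.
- An observed 40% gives t = 1.8/0.626 = 2.87, p = 0.010 (18 df).
- With Bonferroni for three pairs the threshold is 36.7% (18 df), still below 40%.
- The ratio of threshold to detectable difference is 1.315/1.855 = 0.71 and does not depend on the mean or SD. If PBR28 figures gave a 40% detectable difference, the threshold would still be about 0.71 × 40% = 28%.

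**3. Put the two 40% figures on one base.**
- HL mean: 4.5/1.40 = 3.214.
- HH-HL difference: 4.5 − 3.214 = 1.286, and 1.286/4.5 = 28.6% of the HAB mean.
- Detectable difference: 0.40 × 4.5 = 1.8.

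**4. Power for the ER176 difference.**

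| Assumption | n per group | Power |
|---|---|---|
| Equal SD 1.4 | 10 | 49% (18 df), 51% (27 df) |
| Equal SD 1.4 | 11 | 55% (31 df) |
| Constant CV, SD 1.4 v 1.0, Welch | 10 | 60% |
| Log scale, log SD 0.304 | 10 | 65% (18 df), 67% (27 df) |
| Log scale, log SD 0.304 | 11 | 71% (31 df) |

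- Constant CV: 1.4/4.5 = 0.311, and 0.311 × 3.214 = 1.0.
- Log SD: √ln(1 + 0.311²) = 0.304, against ln 1.40 = 0.336.
- Eleven per group is the case where all 34 complete (34/3 = 11.3).
- For scale, 80% power for 1.286 would take about 20 per genotype with equal SD, or 16 with constant CV.

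**5. Width of the HAB-MAB 95% interval, 10 per group.**
- Equal SD: ±1.28 to ±1.32 mL/cm³ (about 29% of the HAB mean).
- Constant CV: SE = √(1.96/10 + 1.0/10) = 0.544; Welch df 16.3; half-width 1.152 (25.6%).

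**The case against.** The best defence is that section 4.1 calls this an exploratory study, the objectives table (section 3) lists V_T without any group test, and no decision in the documents turns on a genotype p-value. The sentence about significance follows directly on a correct statement of 80% power and may be loose wording. Group means, SDs and sizes are the inputs to a Welch interval, and individual values will be listed, so nothing becomes inestimable. All of this stands, and it limits the practical harm. It does not make the sentence correct, and a study that uses power and alpha to justify its cohort can reasonably say how that contrast will be estimated.

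Four stronger readings are tempting, and the documents do not support them.

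- **That contrast, scale and region are all left open.** Section 9.2 indicates HH against the other genotypes, the difference in means, and whole brain as the region of its sizing figures. What is missing is carrying these into 9.4.2, together with an interval and a rule for the two Phase 4 scans.
- **That the plan forecasts a difference of ER176 size.** Section 2.1 says "We predict that the new ¹⁸F-radioligand will be like" ER176 and sensitive to genotype, but gives no magnitude, and it allows for improved performance.
- **That power for the ER176 difference is known to be 50-60%.** The figures run from 49% to 71% and all rest on assumed SDs. The PBR28 mean and SD behind the stated power analysis are not shown. The ER176 figures are consistent with its 40%, which does not show they were the ones used.
- **That HAB-MAB should be the single primary contrast.** It is the only pair with an expected size in 9.2, but 9.2 refers to the other genotypes together, and imaging LABs is part of the rationale in section 2.1.

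**Conclusion.** The statement in 9.2 is wrong as written, and 9.4.2 admits a cheap improvement.

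The significance threshold at 10 per genotype is about 29% of the HAB mean, given the ER176 mean and SD, equal SD and a two-sided test. The 40% figure is right only as the true difference detectable with about 80% power. That distinction survives a different SD and a Bonferroni adjustment for three pairs.

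The ER176 HH-HL difference is 28.6% of the HAB mean, so it is not the difference the design can detect with 80% power. Its power lies between about 49% and 71%, depending on the SD assumption, the scale and the number completing.

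The analysis section omits any estimate or interval for a difference that the synopsis makes part of the primary endpoint and that 9.2 uses for sizing. A reader might infer that the primary endpoint cannot be analysed or that the sample size is miscalculated. Neither follows: the data will exist, and the 40% reproduces. What is lost is a pre-specified estimate with its uncertainty, and a correct account of what 10 per genotype can show.

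**What to change.** **In 9.2:**
- Restate 40% of the HAB mean as the true difference detectable with about 80% power, and remove the claim that it is needed for significance.
- Express the ER176 HH-HL difference on the same base (28.6%, 1.29 mL/cm³) and give its power: about 50% with equal SD, about 60% with constant CV.
- Label the SD in MABs and LABs as an assumption.
- Reconcile the attribution, either by showing the PBR28 mean and SD or by stating that the ER176 figures were used.

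**In 9.4.2:**
- Add the HAB-MAB and HAB-LAB differences in mean whole-brain V_T, each with a 95% Welch interval. These keep the contrast, scale and region of 9.2, and Welch avoids assuming equal SD. Neither contrast needs to be made the sole primary one.
- Use one value per person, with the rule for Phase 4 participants fixed in advance (for example the first scan, which matches Phase 2 in precision, or the mean of the two).
- Keep mean ± SD by genotype as description.

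**Cost:** a few lines of text, with no new data, scans or participants. The HAB-MAB interval will be wide, about ±26% to ±29% of the HAB mean, and the stated power for an ER176-sized difference will be less favourable than 9.2 now suggests. A first-scan rule gives up some precision compared with averaging the two Phase 4 scans.
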